10.4.3 Safety Analyses

- Safety endpoints will be analyzed as summary statistics during treatment
- Adverse events will be coded using the Medical Dictionary for Regulatory Activities
 - Each AE will be counted only once for a given participant
 - Each AE will be presented by System Organ Class
 - The duration, relationship, severity, and outcome of each AE will be reported
 - AE's will be ascertained from adherence and PI-reported
 - AE's leading to premature discontinuation from the study and serious treatment-emergent AE's will be presented in a table

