5.7.2 Handling of Participant Withdrawals or Termination

Patients who withdraw or terminate participation in this study will be called and a follow-up office visit will be set up at 12 weeks regardless of their participation. If the patient refuses to come in, a phone call will be made to discuss adverse events or unanticipated problems over the phone. If a patient is lost to follow-up, two phone calls to the patient and subsequently two phone calls to next-of-kin will be made in an attempt to reach the patient. There is low concern for long-term and short-term safety with either study agent, particularly for the duration of eight weeks only.

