6.1.8 Dose Adjustments/Modifications/Delays

There will be no dose adjustments for the study agent, Revaree. It is not physically possible with this formulation of the drug.

Dose modification for the vaginal estrogen cream, Estrace, may occur if a patient exhibits side effects. If a patient starts to exhibit the most common side effects of breast pain, vaginal spotting, or headache, the dose may be decreased or the treatment may be discontinued depending on the clinical context. If there is any concern for an AE, the treatment may be discontinued. If the patient is responding positively to treatment, the dosing will not be increased.

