7.2.6 Unscheduled Visit

- Obtain patient's reason for visit
- Perform relevant physical exam
- Based on the clinical context, determine whether study agent should be continued or discontinued or modified
- Discuss plan with patient
- Based on the clinical context, document whether patient will continue in study or be removed

CONFIDENTIAL

This material is the property of the NYU School of Medicine and Langone Medical Center. Do not disclose or use except as authorized in writing by the study sponsor
Interventional Template Version: 11 January 2019

Concomitant Medications, Treatments, and Procedures

All concomitant prescription medications taken during study participation will be recorded on the case report forms (CRFs). For this protocol, a prescription medication is defined as a medication that can be prescribed only by a properly authorized/licensed clinician. Medications to be reported in the CRF are concomitant prescription medications, over-the-counter medications and non-prescription medications.

Prohibited Medications, Treatments, and Procedures

Treatment with systemic HRT will not be permitted during or within 6 weeks of starting this study.

Participant Access to Study Agent at Study Closure

HLA is an over the counter medication so patients will have access to the study agent after closure. However, the cost will not be covered after study closure and will be the subject's responsibility, so purchasing the study agent may be cost prohibitive.

8 Assessment of Safety

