8.3 Time Period and Frequency for Event Assessment and Follow-Up

The occurrence of an AE or SAE may come to the attention of study personnel during study visits and interviews of a study participant presenting for medical care, or upon review by a study monitor. All AEs including local and systemic reactions not meeting the criteria for SAEs will be captured on the appropriate RF. Information to be collected includes event description, time of onset, clinician's assessment of severity, relationship to study product (assessed only by those with the training and authority to make a diagnosis), and time of resolution/stabilization of the event. All AEs occurring while on study must be documented appropriately regardless of relationship. All AEs will be followed to adequate resolution.

Any medical condition that is present at the time that the participant is screened will be considered as baseline and not reported as an AE. However, if the study participant's condition deteriorates at any time during the study, it will be recorded as an AE. UPs will be recorded in the data collection system throughout the study.

Changes in the severity of an AE will be documented to allow an assessment of the duration of the event at each level of severity to be performed. AEs characterized as intermittent require documentation of onset and duration of each episode.

The PI will record all reportable events with start dates occurring any time after informed consent is obtained until 7 (for non-serious AEs) or 30 days (for SAEs) after the last day of study participation. At each study visit, the investigator will inquire about the occurrence of AE/SAEs since the last visit. Events will be followed for outcome information until resolution or stabilization.

CONFIDENTIAL

This material is the property of the NYU School of Medicine and Langone Medical Center. Do not disclose or use except as authorized in writing by the study sponsor
Interventional Template Version: 11 January 2019

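### AEs met by an estrogen dose reduction cannot be identified as treatment-limiting, so by-arm counts of AE discontinuations are not like for like

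*Combined protocol and SAP*

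**What the plan says.** **Tabulation.** 10.4.3 says "AE's leading to premature discontinuation from the study and serious treatment-emergent AE's will be presented in a table". The same section also covers all AEs: "Each AE will be presented by System Organ Class", and "The duration, relationship, severity, and outcome of each AE will be reported". It does not say whether the table is split by arm. Retention is calculated within each arm (10.4.4), and the Protocol Summary describes compliance and retention by treatment group.

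**Dose changes.** For HLA, 6.1.8 says "There will be no dose adjustments for the study agent, Revaree". For estrogen, after the common side effects it names (breast pain, spotting, headache), "the dose may be decreased or the treatment may be discontinued depending on the clinical context". Section 7.2.6 has the investigator "determine whether study agent should be continued or discontinued or modified" without naming an arm, and lists continuation in the study as a further item. Section 4.1 says that neither medication is to undergo protocol changes.

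**Data collected.** In 8.3, "Information to be collected includes event description, time of onset, clinician's assessment of severity, relationship to study product", followed by the time of resolution or stabilization. Action taken with the product is not on the list.

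**Follow-up.** For women who withdraw or are terminated, 5.7.2 says "a follow-up office visit will be set up at 12 weeks regardless of their participation".

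**The concern.** Leaving the study because of an AE is an endpoint of management, and the plan gives the arms different routes to it. A woman on estrogen with a troublesome AE may have her dose lowered and remain. A woman on HLA can continue unchanged or stop. If the first woman remains and her AE is not serious, it falls outside the table, and the required AE data do not show that it changed her treatment.

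A second gap applies to both arms. The table is keyed to leaving the study, while 7.2.6 lists the decision on the product and the decision on participation as separate items. A woman who stops the product for an AE but stays to week 12 need not be counted.

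This matters because 10.5 gives the pilot's purpose as assessing feasibility and acceptability and planning a larger trial. AE-driven loss of treatment in each arm is a natural planning input. Formal comparison is not the focus (10.1), but counts shown for two randomised arms will be read side by side.

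**Working it through.** The documents give no AE rate, dose-reduction rate or AE-discontinuation rate, so there is no planned figure to reproduce. The check is a reading of the sections, followed by an illustration on assumed rates.

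**1. Where a non-serious, treatment-limiting AE can go**

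| Management | Estrogen | HLA | In the 10.4.3 table? |
|---|---|---|---|
| Continue unchanged | possible | possible | no |
| Dose reduced, stays in study | allowed (6.1.8) | excluded (6.1.8) | no |
| Product stopped, stays in study | possible | possible | not as worded |
| Leaves the study | possible | possible | yes |

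The second row is open to one arm only. Nothing in the 8.3 list or the per-AE reporting in 10.4.3 separates the first three rows.

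**2. Formula**

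Inputs: 30 women per arm (10.5). Assumed:
- q = share with a treatment-limiting AE, equal in both arms
- r = share of the estrogen cases met by dose reduction, all other estrogen cases leaving the study
- s = share of the HLA cases leaving the study

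Expected tabulated cases are 30 × q × s on HLA and 30 × q × (1 − r) on estrogen. The difference in percentage points is 100 × q × [s − (1 − r)]. HLA shows the larger expected count only if s > 1 − r. The expected number of estrogen cases missing from the table is 30 × q × r, whatever happens on HLA.

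**3. Size when every HLA case leaves (s = 1), r = 50%**

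| q | HLA expected | Estrogen expected | Gap (points) |
|---|---|---|---|
| 2% | 0.6 | 0.3 | 1 |
| 5% | 1.5 | 0.75 | 2.5 |
| 10% | 3.0 | 1.5 | 5 |
| 20% | 6.0 | 3.0 | 10 |

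At q = 20%, r = 25% gives 6.0 against 4.5 (5 points) and r = 75% gives 6.0 against 1.5 (15 points).

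From exact binomials with s = 1, the chance that HLA shows the strictly higher count, moving from r = 0 to r = 50%, rises from 0.377 to 0.555 at q = 5%, from 0.413 to 0.688 at q = 10%, and from 0.436 to 0.821 at q = 20%.

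**4. Direction when some HLA cases stay**

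Ratio of estrogen to HLA tabulated counts, (1 − r)/s:

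| | r = 25% | r = 50% | r = 75% |
|---|---|---|---|
| s = 1 | 0.75 | 0.50 | 0.25 |
| s = 0.75 | 1.00 | 0.67 | 0.33 |
| s = 0.5 | 1.50 | 1.00 | 0.50 |

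True intolerance is equal throughout, so a like-for-like count would give 1. Six of the nine cells are below 1, two equal 1, and one is reversed.

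**The case against.** A reader might infer that the plan reports nothing but discontinuations, that an intolerable AE on HLA can end only in stopping, and that estrogen intolerance will therefore be understated. The documents do not support any of these in full.

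- Serious AEs are in the same table, and every AE is reported by System Organ Class with severity, relationship and outcome. Spotting met by a dose reduction is still reported; what is missing is the label that treatment was changed. This stands.
- An HLA participant may continue through an AE, so the direction depends on s and r. This stands.
- The separation of product from study is not clean. The early-termination visit (7.2.5) has a branch for under 12 weeks of product use, so some women who stop early may be handled as having left. This blurs the second gap but does not close it.
- Large gaps need large rates. Section 2.2.2 describes HLA studies of 10, 100 and 150 women with no side effects reported, and 10.4.5.1 anticipates none for HLA. Rates of 20% or more are hard to square with that, so low rates belong in any illustration. This stands.
- A woman kept in the study on a lower dose has not discontinued. Whether a product can be adjusted is a real property, and discontinuation is itself a relevant planning quantity. This is an argument for separate rows rather than one pooled row.
- Other records exist: the dosing diary (6.1.10), drug reconciliation (6.2), adherence at week 12, and the table of discontinuation reasons (10.4.4), which is not expressly limited to leaving the study. The 8.3 list is also introduced as inclusive, so a form could hold more. But the diary is specified for date and time of dosing, reconciliation does not tie a quantity to an AE, and the reasons table depends on a reason being given and has no place for a dose reduction. Nothing requires the link to be made.

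**Conclusion.** The point holds as a reporting gap. By-arm counts of AEs leading to study discontinuation are not like for like, because dose reduction is open to estrogen only and the action taken with the product is not a required data item. AEs that stop the product in a woman who stays in the study share the problem in both arms.

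Understatement of estrogen intolerance relative to HLA is likely but not established. On the simplification that estrogen cases not dose-reduced all leave, it requires s > 1 − r. The size is unknown: 1 point at q = 2% and 10 points at q = 20% with r = 50% and s = 1, all of these being assumed rates. At low rates the difference is a fraction of one woman in 30.

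No primary or secondary efficacy analysis is affected, and the plan defines no tolerability endpoint. This is a cheap improvement to a descriptive pilot. It is worth making before data collection because the link between an AE and a dose change may not be recoverable reliably afterwards.

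**What to change.** 1. In 8.3, add one AE field: action taken with study product (none / dose reduced / interrupted / stopped).
2. In 10.4.3, keep the serious-AE rows and tabulate by randomised arm, as separate rows, AEs leading to dose reduction, to interruption, to stopping the product, and to leaving the study. State that the first three are counted whether or not the woman remains in the study. Any combined row should be a supplementary description and not the main comparison, since HLA has no dose-reduction option.
3. Reconcile 4.1 with 6.1.8 and 7.2.6 on whether, and in which arm, the product may be modified. No position is taken here on which dosing rule is right.

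Cost: one extra form field and a longer table that shows more AEs. No additional visits or participants are needed.

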10.4.4 Adherence and Retention Analyses

Due to the nature of this study, study agent usage will be assessed solely by patient self-report. Participation and study retention will be assessed by a ratio of those who participated divided by the total starting cohort for that study arm. Those that discontinue and provide a reason for discontinuation will be categorized and the information will be presented in a table.

10.4.5 Planned Interim Analysis

No interim analyses are planned.

10.4.5.1 Safety Review

There are no anticipated side-effects to the investigational agent. The control agent is FDA approved for the condition being studied in this trial. Thus, study enrollment will only be stopped if unforeseeable, significant side effects or life-threatening adverse events occur in either study cohort. No statistical rules will be used to halt enrollment due to the short duration of the study and lack of interim analysis.

Patients will be counseled at the start of the study to call [name] or [name] for any side-effect or AE they believe is related to study medication usage. Otherwise, after the baseline visit, the next formal visit will be the final visit at week 12 when medication safety questions will be asked.

10.4.6 Additional Sub-Group Analyses

Due to the small cohort size of this pilot study, there will be no sub-group analysis.

10.4.7 Exploratory Analyses

N/A

CONFIDENTIAL

This material is the property of the NYU School of Medicine and Langone Medical Center. Do not disclose or use except as authorized in writing by the study sponsor
Interventional Template Version: 11 January 2019

10.5 Sample Size

This study would be the first US-based randomized trial investigating HLA's usage for GSM treatment, to the authors' best knowledge. Thus, the sample size of 60 has been chosen to pilot the presented protocol, to assess feasibility and acceptability in quality of life for HLAs and to gather preliminary effectiveness for planning a larger effectiveness trial. The authors acknowledge the limitations of having enrolling 60 individuals, including generalizability. However in this initial stage of study implementation and design, expect this number to provide sufficient information.

No study to date has used the VSQ to assess the impact of treatment modalities for GSM, so there is no historical data to provide an assumed mean score. However, with 30 individuals randomized to each study treatment, we expect to have at least 80% probability of achieving a 95% confidence interval (CI) width of 1.7, assuming a standard deviation in the VLM of 2. With fewer individuals at any timepoint, the width of the CI will increase.

The assumed drop-out, withdrawal, cross-over and missing data rate is assumed to be 33%, which explains the enrollment goal of 60 to allow for 40 evaluable patients. This is a conservative estimate because the missing data rates in RCT's from four major journals has shown to be 20% or greater in about 18% of trials, which was also seen in quality-of-life studies (26, 27). We will monitor reasons for drop out and withdrawal of treatment to improve study adherence and follow up.

All participants will be included in the intent to treat analyses, and those participants who use the study intervention for at least 12 weeks will be included in the per-protocol analysis.

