5.6 Total Number of Participants and Sites

Recruitment will end when approximately 60 participants are enrolled at this single site at NYUMC. It is expected that approximately 60 participants will need to be enrolled in order to retain 40 evaluable participants at 12 weeks of follow up (an overall 33% drop out rate).

CONFIDENTIAL

This material is the property of the NYU School of Medicine and Langone Medical Center. Do not disclose or use except as authorized in writing by the study sponsor
Interventional Template Version: 11 January 2019

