7.2.5 Withdrawal/Early Termination Visit

If 12 weeks of study agent usage:

- Record AE as reported by participant or observed by investigator
- Record participant's adherence to treatment regimen
- Obtain GSM symptom history, and record VAS scores for dyspareunia, itching, and dryness
- Record vital signs, results of physical exam including pelvic
- Collect pelvic samples for vaginal pH and vaginal tissue scraping for vaginal maturation index
- Have patient fill out VSQ
- Discuss the obvious, preliminary changes in their symptoms, if any exist
- Provide contact information for [name] to communicate any AE or side-effect experienced after the end of the study if patient believes it is related to the study

If <12 weeks of study agent usage:

- Record AE as reported by participant or observed by investigator
- Record participant's adherence to treatment regimen
- Record vital signs, results of physical exam including pelvic
- Provide contact information for [name] to communicate any AE or side-effect experienced after the end of the study if patient believes it is related to the study

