10.2 Statistical Hypotheses

We expect no clinically meaningful differences in baseline characteristics or baseline assessment of outcomes between those randomized to HLA or to vaginal estrogen, however this is possible given the limited pilot trial sample size. These differences will be assessed and considered in the evaluation of outcomes for primary and secondary endpoints.

We expect a clinically meaningful improvement in the change measured at 12 weeks (comparison of VSQ at 12 weeks, adjusted for baseline) in VSQ in the HLA group, and expect this to be greater as compared to those randomized to vaginal estrogen. Similarly, we expect to observe clinically meaningful improvements in the HLA group at 12 weeks, beyond those observed in those randomized to the vaginal estrogen cohort. These include VSI, FSFI, VAS for dyspareunia, itching, and dryness, vaginal pH, and presence of rugal folds.

CONFIDENTIAL

This material is the property of the NYU School of Medicine and Langone Medical Center. Do not disclose or use except as authorized in writing by the study sponsor
Interventional Template Version: 11 January 2019

These estimates will provide estimates for establishing effectiveness in future trials.

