10.4 Description of Statistical Methods

Baseline (pre-randomization) participant demographics and clinical characteristics will be summarized through descriptive statistics overall, and by randomized group. Clinical characteristics will include past HRT use, uterus present or not, and components of their medical and gynecologic history. Details of each outcome measure is provided below. Analysis of the primary and secondary measures will include summarizing each by the mean and standard deviation at baseline and all measured time points, including at the primary outcome time of 12 weeks. For continuous measures, a linear mixed effects regression model will estimate the mean outcome at 12 weeks, both unadjusted and adjusted for baseline measurement. No further adjustment for participant characteristics is expected given the limited trial size. The linear mixed effects regression model will allow all participants to be included in analysis, regardless of completion of study follow up at 12 weeks, under the assumption of this assessment being missing at random.

Missing outcome data will be summarized by participant characteristics to understand how to better retain individuals in treatment.

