10.6 Measures to Minimize Bias

10.6.1 Enrollment/Randomization/Masking Procedures

While blinding would be desired in this study, it is not feasible due to the study drugs having different formulations. Therefore, once randomization is performed, investigators and patients will know which study arm patients are assigned to. The implication of lack of blinding is that there could be potential bias regarding patient report of symptomatic improvement and provider record of measurements, such as VAS scores. However, the goal of this study is to be a pilot study to allow for a larger RCT in the future that could potentially be blinded and allow for minimization of biases.

To reduce bias, randomization will be used with allocation 1:1 to each treatment group. Block randomization will be used due to the small sample size of each study arm using Trialmaster. Replacement of patients who discontinue will not be allowed since the enrollment goal of 60 is conservative to account for drop-outs, early discontinuation, and lost to follow up patients.

11 Source Documents and Access to Source Data/Documents

Source data is all information, original records of clinical findings, observations, or other activities in a clinical trial necessary for the reconstruction and evaluation of the trial. Source data are contained in source documents. Examples of these original documents, and data records include: hospital records, clinical and office charts, laboratory notes, memoranda, subjects'

CONFIDENTIAL

This material is the property of the NYU School of Medicine and Langone Medical Center. Do not disclose or use except as authorized in writing by the study sponsor
Interventional Template Version: 11 January 2019

diaries or evaluation checklists, pharmacy dispensing records, recorded data from automated instruments, copies or transcriptions certified after verification as being accurate and complete, microfiches, photographic negatives, microfilm or magnetic media, x-rays, subject files, and records kept at the pharmacy, at the laboratories, and at medico-technical departments involved in the clinical trial. It is acceptable to use CRFs as source documents. If this is the case, it should be stated in this section what data will be collected on CRFs and what data will be collected from other sources.

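### The only precision figure in 10.5 assumes 30 measured women per arm, but the plan expects about 20, where the chance of meeting it unadjusted is about 32%

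*Combined protocol and SAP*

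**What the plan says.** Section 10.5 gives one precision statement, for 30 women randomized to each treatment: "at least 80% probability of achieving a 95% confidence interval (CI) width of 1.7, assuming a standard deviation in the VLM of 2". It adds one caveat without a number: "With fewer individuals at any timepoint, the width of the CI will increase".

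The next paragraph of 10.5 assumes that 33% will be lost to drop-out, withdrawal, cross-over and missing data, "which explains the enrollment goal of 60 to allow for 40 evaluable patients". Section 5.6 places those women at the primary timepoint: "approximately 60 participants will need to be enrolled in order to retain 40 evaluable participants at 12 weeks of follow up". Section 10.6.1 sets 1:1 allocation and states: "Replacement of patients who discontinue will not be allowed since the enrollment goal of 60 is conservative".

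Two further passages bear on the point:
- Section 7.2.5, under "If <12 weeks of study agent usage", lists adverse events, adherence, vital signs and examination, but no VSQ.
- The analysis is to be baseline-adjusted in part. Section 10.2 describes a "comparison of VSQ at 12 weeks, adjusted for baseline", and the mixed model in 10.4 will "estimate the mean outcome at 12 weeks, both unadjusted and adjusted for baseline measurement".

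**The concern.** The precision figure assumes that every randomized woman contributes a week-12 score. The same section expects a third of them to be lost and uses that loss to justify enrolling 60. The only quantitative support for the sample size therefore describes a case that the plan does not expect.

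The statement is also hard to interpret. It does not say whether the interval is for one arm's mean or for the difference between arms, although 10.1 promises treatment effects with 95% intervals. The SD is attached to VLM, which is not defined anywhere and in context appears to mean the VSQ. Nothing says whether 2 is the SD of the score, of the change (the primary endpoint in 4.2.1) or of the baseline-adjusted residual.

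The pilot's product is a set of estimates with 95% intervals for planning a larger trial. A reader of 10.5 would expect narrower intervals than the planned number of evaluable women supports without adjustment.

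**Working it through.** **Inputs from the documents.** 95% confidence, target width 1.7, probability 80%, SD 2, 30 randomized per arm (10.5); 33% loss and 40 evaluable (10.5, 5.6); 1:1 allocation (10.6.1). The enrolment step reproduces: 40 / (1 − 0.33) = 59.7, or 60. Assumption: loss is equal between arms, so 20 per arm.

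**Formulas, unadjusted within-arm t-interval.**
- Width at the assumed SD: W = 2 × t(0.975, n−1) × SD / √n
- Width reached with 80% probability: W × √[χ²(0.80, n−1) / (n−1)]
- P(width ≤ 1.7) = χ² CDF with n−1 df, evaluated at (n−1)(1.7/W)²

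**The plan's own figure, n = 30.** W = 2 × 2.045 × 2 / √30 = 1.494. The χ² argument is 29 × (1.7/1.494)² ≈ 37.6 on 29 df, so P = 0.868. At least 80% is correct.

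**The planned evaluable number, n = 20.** W = 2 × 2.093 × 2 / √20 = 1.872. The χ² argument is 19 × (1.7/1.872)² ≈ 15.7 on 19 df, so P = 0.321. The 80% width is 1.872 × √(23.90/19) = 2.10.

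| n per arm | W at SD 2 | 80% width | P(width ≤ 1.7) |
|---|---|---|---|
| 30 | 1.494 | 1.644 | 0.868 |
| 29 | 1.522 | 1.677 | 0.829 |
| 28 | 1.551 | 1.712 | 0.784 |
| 24 | 1.689 | 1.878 | 0.557 |
| 20 | 1.872 | 2.100 | 0.321 |

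The 80% survives the loss of one woman per arm but not two; the plan expects to lose about ten. Pooling the variance over both arms at 20 per arm (38 df) leaves P at 0.322. The row for 24 is shown because the 33% counts cross-overs, who may still be measured.

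**Within-arm or between-arm?** For the difference between arms (pooled t, standard error SD × √(2/n)), P(width ≤ 1.7) is 0.028 at 30 per arm and 0.001 at 20. A full width of 1.7 therefore fits only a within-arm interval. At 20 per arm the between-arm 80% width is 2.79.

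**Effect of baseline adjustment, if 2 is the raw-score SD.** Fit each arm separately at its mean baseline, with SD 2√(1−r²) and n−2 df. Here r is the baseline to week-12 correlation; every value is an assumption.

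| r (n = 20) | W | 80% width | P(width ≤ 1.7) |
|---|---|---|---|
| 0.4 | 1.722 | 1.937 | 0.514 |
| 0.5 | 1.627 | 1.830 | 0.647 |
| 0.6 | 1.503 | 1.690 | 0.810 |

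P reaches 0.80 at r = 0.594, or at r = 0.510 with one model pooled over both arms (37 df).

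**Unadjusted mixed model using all 30 baselines.** The approximate standard error is 2√[(1−r²)/20 + r²/30], with 19 df. P is 0.380, 0.416, 0.464 and 0.526 at r = 0.4, 0.5, 0.6 and 0.7.

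**If the SD means something else.**
- SD of change: 0.321 stands for an unadjusted completer interval for the change.
- Residual SD: the adjusted fit gives 0.320 (18 df).
- Raw-score SD, interval for change (SD of change 2√[2(1−r)]): at r = 0.4, P is 0.649 at n = 30 and 0.164 at n = 20; at r = 0.6 it is 0.981 and 0.580.

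**The case against.** The strongest reply is that nothing stated is numerically wrong. The sentence is conditional on 30 per arm, the section says that fewer women widen the interval, and the loss rate and the 40 evaluable follow at once. That is true, and this point does not call the 86.8% case an error. The caveat, however, is general. The loss to 40 is the base case, and no figure is given for it.

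Second, 32% is the least favourable of the planned analyses. The mixed model keeps all randomized women, and a baseline-adjusted estimate is planned. This stands in part. Women with a baseline score only do not replace missing week-12 scores: the unadjusted mixed model reaches only 38% to 53% at assumed correlations of 0.4 to 0.7. Adjustment could close the gap entirely, but only with a sufficient correlation and a raw-score SD of 2, and the documents establish neither.

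Third, 20 measured per arm may be pessimistic. The 33% includes cross-overs, 10.5 calls it conservative, and 5.7.2 arranges a 12-week visit for women who withdraw. Section 7.2.5 lists no VSQ for those with under 12 weeks of use, so whether they would be scored is unclear. At 24 per arm the unadjusted figure is still 56%, although with adjustment at an assumed r of 0.5 (raw-score SD, separate fits) it would be 87%. Section 5.6 itself gives 40 evaluable at 12 weeks.

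Finally, this is a pilot: formal comparison is not its focus and no rule requires a width of 1.7. That stands, and it limits the consequence.

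**Conclusion.** The concern holds. The stated precision is right for 30 measured women per arm, but the plan expects about 20, and 10.5 gives no figure for that number. For an unadjusted within-arm interval in completers at SD 2, with equal loss, the chance of a width of 1.7 or less falls from 86.8% to about 32%. The 80% width rises from 1.64 to 2.10, which is (2.10 − 1.64)/2 = 0.23 points on each side of a 0 to 21 scale.

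How much of this remains after baseline adjustment cannot be settled from the documents. If 2 is the raw-score SD, the shortfall ranges from substantial to none, and it disappears at a correlation of about 0.59 or more (0.51 if pooled over arms).

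This should be fixed, but it is a matter of an unclear and optimistic precision statement. No test or decision rule depends on it, and the design does not fail because of it.

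**What to change.** Reword 10.5 as follows.

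1. State whether the SD of 2 is for the VSQ score, its change or the baseline-adjusted residual, and give its basis. Replace VLM with the variable meant, apparently the VSQ.
2. Say that the interval is within-arm.
3. Give the precision at the planned evaluable number. If the SD of 2 applies to the quantity being estimated, suitable text would be: *With 20 evaluable women per arm and an SD of 2, there is 80% probability that the unadjusted within-arm 95% CI is no wider than 2.1 (between-arm: 2.8); baseline adjustment may narrow this.* The figure for 30 per arm can stay beside it, labelled as the full-retention case.
4. If credit is to be taken for baseline adjustment, state the assumed correlation and its source, and show a range.

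The cost is wording only: no extra women and no change to enrolment or analysis. The stated precision becomes less favourable unless a baseline correlation can be justified.
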